3. INTRODUCTION

As per ICH E9 ([1](#)), the purpose of this document is to provide a more technical and detailed elaboration of the principal features of the analysis described in the CTP and its amendments, and to include detailed procedures for executing the statistical analysis of the primary and secondary variables and other data.

This TSAP assumes familiarity with the CTP. In particular, the TSAP is based on the planned analysis specification as written in CTP Section 7 “Statistical Methods and Determination of Sample Size”. Therefore, TSAP readers may consult the CTP for more background information on the study, e.g., on study objectives, study design and population, treatments, definition of measurements and variables, and planning of sample size, and randomization.

The statistical analyses will be performed within the validated working environment CARE, including SASTM (current Version 9.4, by SAS Institute Inc., Cary, NC, USA), and a number of SASTM-based tools (e.g., macros for the analyses of AE data or laboratory data; Report Appendix Generator system (RAGe) for compilation/formatting of the CTR appendices).

Study data will be stored in a trial database within the BRAVE system.

Analyses of the biomarker and gene expression data are described in a separate biomarker TSAP, unless otherwise specified in this document.

This is a multicenter, randomized, double-blind, placebo-controlled Phase II study with one dose of Spesolimab/placebo in patients with GPP presenting with an acute flare of moderate to severe intensity. In total, at least 51 patients will be randomized to receive Spesolimab/ placebo (2:1). All patients will receive the dose of study medication (900 mg i.v. Spesolimab or Placebo) on Day 1 of Week 1. Based on the subsequent treatment response, patients will then be followed for 12 to 28 weeks (see Flow Chart of CTP). The primary and key secondary efficacy endpoints of the trial will be determined on Day 8. This TSAP fully specifies the analyses of the trial.

4. CHANGES IN THE PLANNED ANALYSIS OF THE STUDY

Following further endpoints are added to TSAP:

- Change from baseline in GPPGA total score, by visit
- Change from baseline in GPPGA pustulation subscore, by visit
- GPPGA clear/almost clear (modified) defined as a GPPGA total score of 0 or 1 and with all subscores < 3, by visit
- A GPPGA erythema sub-score of 0 or 1, by visit.
- A GPPGA scaling sub-score of 0 or 1, by visit.
- A GPPGA pustulation sub-score drop by at least 2 points from baseline, by visit.
- A Pain VAS drop by at least 30 points from baseline.
- Percentage change from baseline in each of GPPASI pustulation, erythema and scaling severities.
- [REDACTED]
- A PSS score of 0, by visit
- A FACIT-Fatigue score improvement of at least 4 points, by visit

For time to first achievement of GPPGA pustulation score of 0 or GPPGA score of 0 or 1, the first day should be day of randomized treatment if it is different from randomization. For Wilcoxon testing, the calculations of ranks should be also relative to Day 1.

Percentage change from baseline in GPPASI will be calculated instead of percentage reduction in GPPASI. For example, if there is 50% reduction in GPPASI score, it means % change from baseline in GPPASI is -50%.

5. ENDPOINTS

5.1 PRIMARY ENDPOINT

The primary endpoint of the study is:

- A GPPGA pustulation subscore of 0 indicating no visible pustules at Week 1.

For the estimand concept (EN) on the above-defined primary binary endpoint definition, death or any use of escape medication prior to week 1 will be considered to represent a non-response at the Week 1 timepoint.

See [Section 9.1.2](#) for further details on the derivation of the GPPGA total score.

5.2 SECONDARY ENDPOINTS

Key Secondary Endpoint

- A Generalized Pustular Psoriasis Physician Global Assessment (GPPGA) score of 0 or 1 at Week 1.

The same estimand concept (EN) used for primary endpoint will be used for key secondary endpoint.

Secondary Endpoints at Week 4 (included in the statistical testing strategy):

Secondary endpoints of the study at Week 4 which are included in the statistical testing strategy in a hierarchical manner subsequent to performance of the tests on the primary and key secondary endpoints are:

- A Psoriasis Area and Severity Index for Generalized Pustular Psoriasis (GPPASI) 75 at Week 4.
- Change from baseline in Pain Visual Analog Scale (VAS) score at Week 4.
- Change from baseline in Psoriasis Symptom Scale (PSS) score at Week 4.
- Change from baseline in Functional Assessment of Chronic Illness Therapy (FACIT) Fatigue score at Week 4.

Secondary Endpoints at Week 4 (not included in the statistical testing strategy):

- A Generalized Pustular Psoriasis Physician Global Assessment (GPPGA) score of 0 or 1 at Week 4.
- A GPPGA pustulation sub-score of 0 indicating no visible pustules at Week 4.
- A GPPASI 50 at Week 4.
- The percent change from baseline in GPPASI at Week 4.

Secondary Endpoints at Week 1:

- A GPPASI 50 at Week 1.

[figure not shown]
- The percent change from baseline in GPPASI at Week 1.

[figure not shown]
For the estimand concept (EN) on each of the above-defined binary and continuous secondary endpoint definition(s) at week 1/4, death or any use of escape medication prior to week 1/4, or OL Spesolimab use at D8 or any rescue medication with Spesolimab prior to week 4 will be considered to represent a non-response at the week 1/4 time-point.

[figure not shown]
For further details on the derivation of the GPPASI score, the PSS score, and the FACIT-Fatigue score, refer to [Sections 9.1.1, 9.1.5](#), and [9.1.3](#), respectively.

[figure not shown]
Secondary Safety Endpoints:

[figure not shown]
- The occurrence of Treatment Emergent Adverse Events (TEAEs).

6. GENERAL ANALYSIS DEFINITIONS

6.1 TREATMENTS

For basic study information on the treatment to be administered, assignment to treatment, and selection of dose, cf. Section 4 of the CTP.

The study phases are defined relative to randomized dose at Day 1 as below:

Table 6.1: 1 Flow chart of analysis phases of the study according to randomized treatment

Study analysis phase	Description	Start (included)	End (included)
Screening phase	Screening	Earliest of (Date of informed consent, first screening procedure)	Date/time of start of infusion of randomized study treatment minus 1 minute
Treatment phase (including Residual effect period) ²	On-treatment period	Date/time of start of infusion of randomized study treatment (Day 1)	Earliest of: i) Date of end of infusion of randomized study treatment (Day 1) + 112 days at 23:59, ii) Date/time of first dose in OLE trial 1368.25., iii) Date of end-of-study visit if there is no roll-over to 1368.25
Follow-up phase ¹²	Off-treatment period	Date of end of infusion of randomized study treatment (Day 1) + 113 days at 0:00	Latest of: i) Date of End-of-Study visit; ii) last contact date on End of Study page at 23:59

Dates are defined individually per patient. An analysis phase will not extend beyond the start date of the following phase.

¹ The off-treatment period (i.e. Follow-up phase) only exists if the last contact date is after the date of end of infusion of randomized treatment + 112 days.

² For primary safety purpose, safety data is censored for reporting following intake of (optional) open-label Spesolimab on Day 8, or intake of rescue medication with Spesolimab for treatment of a GPP flare.

Treatment groups for the analysis phases according to the randomized/actual treatment on Day 1 (see [Table 6.1: 1](#)) will be labelled as follows:

- **"Placebo"** (i.e. randomized to receive /actual received Placebo on Day 1)
- **"Speso 900 mg IV SD"** (i.e. randomized to receive /actual received Spesolimab on Day 1)
- **"Overall"**(across treatments), where appropriate.

“Overall Total” is applicable in disposition, demographics and baseline characteristics, compliance summaries, AE, clinically significant abnormal lab values and others if needed. Where applicable, output columns should be arranged in the order as given above.

For analysis on effects of OL Spesolimab at Day 8 following randomized treatment at Day 1, patients will be categorized into four different groups (see [Section 7.6.2](#)):

- **Arm 1, "Placebo only"**(i.e. randomized to placebo treatment and not given OL Spesolimab at D8)
- **Arm 2, "Placebo + OL D8"**(i.e. randomized to placebo treatment and given OL Spesolimab at D8)
- **Arm 3, "Speso only"**(i.e. randomized to Spesolimab treatment and not given OL Spesolimab at D8)
- **Arm 4, "Speso + OL D8"**(i.e. randomized to Spesolimab treatment and given OL Spesolimab at D8)

For further analysis on safety data including REP of any non-randomized Spesolimab, individual patient's data will be separated based on the use of randomized treatment at Day 1 and non-randomized Spesolimab as follows (see [Section 7.8.1](#)):

- **“Prior non-rand. Speso ”**(i.e. TEAE starting before use of any non-randomized Spesolimab are considered)
- **“Post OL Speso at D8”** (i.e. TEAE starting post OL dose at Day 8 but before rescue medication with Spesolimab are considered)
- **“Post rescue with Speso”** (i.e. TEAE starting post rescue medication with Spesolimab are considered)

More details on the technical implementation of these analyses are provided in the ADS Plan of this TSAP.

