4.2 OTHER TREATMENTS, EMERGENCY PROCEDURES, RESTRICTIONS

4.2.1 Other treatments and emergency procedures

Stable doses of concomitant therapies for chronic conditions, for which neither the condition nor the treatment are judged to exclude the patient from participation (see [Section 3.3](#)), are permissible. All concomitant medications should be carefully evaluated by the investigator and the Local Clinical Monitor (CML) should be contacted when there are questions regarding concomitant medications.

During the trial, if the severity and progression of the disease worsens, the investigator can treat the patient with Standard of Care (escape treatment) of his/her choice. Please refer to [Table 3.1:1](#) for the details on the use of escape treatment during the trial. All efforts should be made to inform the patient of the importance of coming to the protocol specified visits (See [Flow Chart](#)) up to the EoS visit. Patients refusing to return to the study site (during the follow-up period) should at least provide safety information by phone at the respective visits.

Overall, the choice of the escape treatment i.e Standard of Care (SoC) treatment will be left at the discretion of the investigator. The sponsor will not provide/supply SoC treatment (s) to the sites.

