7.3.5 Safety analyses

Adverse events will be coded using the current version of Medical Dictionary for Regulatory Activities (MedDRA) coding dictionary. Standard BI summary tables and listings will be produced.

All treated patients will be included in the safety analysis. In general, safety analyses will be descriptive in nature and will be based on BI standards. No hypothesis testing is planned. Statistical analysis and reporting of adverse events will concentrate on treatment-emergent adverse events. To this end, all adverse events occurring between start of treatment and end of the residual effect period will be considered 'treatment-emergent'; the residual effect period (REP) is defined as 16 weeks after the last dose of trial medication. Note that for patients who continue into the extension trial, TEAE up to the first dose in the extension trial will be available for display in the current study. Adverse events that start before first drug intake and deteriorate under treatment will also be considered as 'treatment-emergent'. For all subjects who received OL BI 655130 at D8 or rescue medication with BI 655130, safety assessments including adverse events, laboratories, vital signs etc. which occurred subsequent to such intake will be excluded from presentations according to the planned treatments; these data will, however, be included in summaries where all data after any use of BI 655130 are displayed.

Frequency, severity, and causal relationship of adverse events will be tabulated by system organ class (SOC) and preferred term after coding according to the current version of the MedDRA.

The exposure adjusted incidence rate (per 100 subject years) of a selected treatment emergent adverse event is defined as the number of subjects experiencing the adverse event per treatment group during time at risk divided by the total time of subjects at risk in that treatment group to contribute the event to the analysis multiplied by 100 (per 100 subject years), where:

[figure not shown]
$$\text{Time at risk [subject years]} = (\text{date of onset of TEAE} - \text{study drug start date} + 1) / 365.25$$

[figure not shown]

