7.8.1 Adverse events

AEs will be coded with the most recent version of MedDRA. Patients will be analyzed according to the actual treatment received.

The exposure adjusted incidence rate (per 100 subject years) of a selected treatment emergent adverse event is defined as the number of subjects experiencing the adverse event per treatment group during time at risk divided by the total time of subjects at risk in that treatment group to contribute the event to the analysis multiplied by 100 (per 100 subject years).

Incidence rate [1/100 Subject years (pt-yrs)] = $100 * \frac{\text{number of subjects with AE}}{\text{Total AE-specific time at risk [subject years]}}$.

For analysis up to Week 1, Week 12 and the end of REP of randomized drug:

Time at risk [subject years] = (date of onset of TEAE up to the end time of risk – randomized study drug start date + 1) / 365.25

The end time of risk will be the min (day of death, randomized drug stop date + X days, the day prior to OL Spesolimab at Day 8, the day prior to rescue medication with Spesolimab, the day prior to first dose in the extension study if patient will be rolled over or last contact date

per EoS page if patient will not be rolled over). Here X equals to 6, 84 and 112 for analysis up to Week 1, Week 12 and the end of REP of randomized drug respectively.

For the further analysis on safety data,

Time at risk prior to non-randomized Spesolimab/ post OL Spesolimab at Day 8/post rescue medication with Spesolimab [subject years] = (date of onset of TEAE up to the end time of risk – randomized treatment date/Day 8 / date of rescue use of Spesolimab + 1) / 365.25

End of time at risk prior to any non-randomized Spesolimab will be the min of (Day 113 or the day prior to any non-randomized Spesolimab, last contact date per EoS page if patient will not be rolled over or the day prior to first dose in the extension study if patient will be rolled over).

End of time at risk post OL Spesolimab at Day 8 will be the min of (Day 8 Spesolimab date +112 or the day prior to the use of rescue medication with Spesolimab or the last contact date per EoS page if patient will not be rolled over or the day prior to first dose in the extension study if patient will be rolled over).

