End of time at risk post use of rescue medication with Spesolimab will be the min of (the day of rescue medication with Spesolimab in the trial +112 or the last contact date per EoS page if patient will not be rolled over or the day prior to first dose in the extension study if patient will be rolled over).

In addition, for overall period post use of any Spesolimab,

Time at risk overall post use of any Spesolimab [subject years] = (date of onset of TEAE up to the end time of risk – first use of any Spesolimab start date + 1) / 365.25

End of time at risk for overall post use of any Spesolimab will be min of (the day of last Spesolimab in the trial +112 or the last contact date per EoS page if patient will not be rolled over or the day prior to first dose in the extension study if patient will be rolled over).

The analyses of AEs will be descriptive in nature. All analyses of AEs will be based on the exposure adjusted incidence rates (per 100 subject years), as well as the number of patients with AEs and not on the number of AEs. System organ classes (if applicable) will be sorted according to the standard sort order specified by the EMA, preferred terms (if applicable) will be sorted by total frequency (within system organ class) across all treatment columns, cf. [Section 6.1](#).

For further details on summarization of AE data, please refer to "Handling and summarization of adverse event data for clinical trial reports and integrated summaries" ([7](#)) and "Handling of missing and incomplete AE dates" ([4](#)).

The analysis of AEs will be based on the concept of treatment emergent AEs. This means that all AEs will be assigned to the screening phase, treatment phase or follow-up phase as

defined in [Section 6.1](#). Since only the start date of an AE is collected (without start time), any AE occurrence on the same day as randomized Spesolimab/placebo administration will be assigned to the on-treatment period.

An overall summary of AEs will be presented. This overall summary will include summary for the class of AESIs.

The following are considered as AESIs ([see Sec 5.2.6.1 of CTP](#)):

- Hepatic injury
- Systemic hypersensitivity reactions including Infusion reactions and anaphylactic reaction
- Severe infections (according to RCTC grading in the ISF)
- Opportunistic and mycobacterium tuberculosis infections

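### SAP Table 6.1: 1 and SAP 7.8.1 end the same on-treatment window on different dates, so a little risk time can lie in no analysis phase and crude and rate tables can disagree on the first extension-dose day

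*SAP*

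**What the plan says.** SAP 7.8.1 takes treatment-emergence from the phases in SAP 6.1: "all AEs will be assigned to the screening phase, treatment phase or follow-up phase". Table 6.1: 1 ends the treatment phase, end included, at the earliest of three dates:

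- "Date of end of infusion of randomized study treatment (Day 1) + 112 days at 23:59"
- "Date/time of first dose in OLE trial 1368.25"
- "Date of end-of-study visit if there is no roll-over to 1368.25"

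The follow-up phase starts at a fixed point, "Date of end of infusion of randomized study treatment (Day 1) + 113 days at 0:00". A footnote says it exists only if last contact is later than 112 days after the infusion. It ends at the later of the EoS visit and the last contact date, so the table itself treats these as two dates.

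For the rate, SAP 7.8.1 ends time at risk at a minimum of several dates. One is the randomized drug stop date plus X days (X = 6, 84 or 112). Another is "the day prior to first dose in the extension study if patient will be rolled over or last contact date" on the EoS page, the latter for patients who do not roll over. The numerator is subjects with the event during time at risk. Onset times of adverse events are not collected, only dates.

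Protocol 7.3.5 says that "all adverse events occurring between start of treatment and end of the residual effect period will be considered" treatment-emergent, with a residual effect period of 16 weeks and no cut at the EoS visit. It censors time at risk at last contact for patients who do not roll over, and at the first extension dose for those who do.

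**The concern.** The treatment-emergent phase decides which events can be counted. Time at risk decides the denominator. If they end on different dates for one patient, the denominator can include days in which no event can be counted, or an event can enter one table and not the other.

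SAP 7.8.1 says that every event is assigned to a phase. For an event after an EoS visit before Day 113, and dated before Day 114, no phase is available. The sentence below the table that a phase does not extend past the start of the next one only shortens phases, so it does not fill the gap. The EoS-visit clause also departs from Protocol 7.3.5, and SAP Section 4 does not list it among the changes to the planned analysis.

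Occurrence of treatment-emergent events is a defined secondary safety endpoint, and all adverse event analyses report both patient counts and rates per 100 subject-years.

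**Working it through.** **The shared cap.** 16 weeks × 7 = 112 days. Day 1 + 112 = Day 113, and follow-up starts at Day 1 + 113 = Day 114. This agrees with SAP Table 6.7: 1, where off-treatment starts on Day 114. With X = 84 and 112, time at risk ends at the latest on Day 85 and Day 113. The cap is consistent in both places.

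**Rules as written, in day numbers, leaving aside death and open-label or rescue doses.**

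- Phase end = min(113, first extension-dose day) with roll-over, or min(113, EoS visit day) without.
- Risk end = min(1 + X, first extension-dose day − 1) with roll-over, or min(1 + X, last contact day) without.

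**Without roll-over.** The documents give no interval between EoS visit and last contact, so the dates below are assumed. The phase end shown is capped at 1 + X.

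| EoS visit | Last contact | X | Phase end | Risk end | Risk days outside the phase | Phase end / risk end |
|---|---|---|---|---|---|---|
| 106 | 106 | 112 | 106 | 106 | 0 | 1.00 |
| 106 | 113 | 112 | 106 | 113 | 7 | 0.94 |
| 110 | 117 | 112 | 110 | 113 | 3 | 0.97 |
| 30 | 60 | 112 | 30 | 60 | 30 | 0.50 |
| 106 | 113 | 84 | 85 | 85 | 0 | 1.00 |
| 60 | 90 | 84 | 60 | 85 | 25 | 0.71 |

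The last column is for one event-free patient's own time. For an arm with T risk days in total, of which g lie outside the phase, the rate is multiplied by (T − g)/T, which is much closer to 1 when few patients are affected.

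**Which analyses are touched.** The flow chart places the EoS visit of patients not entering the extension 16 weeks ± 7 days after the last trial dose. That is Day 113 ± 7, or Days 106 to 120, if only the Day 1 dose was given. An on-schedule visit on Days 106 to 112 can therefore create a gap of up to 113 − 106 = 7 days in the residual-effect-period analysis. It cannot affect the Week 12 analysis, which stops at Day 85; there the visit must be before Day 85, which means early discontinuation.

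**With roll-over.** First extension dose on Day 85: phase end 85, risk end 84. First extension dose on Day 99: phase end 99, risk end 98 (X = 112). The difference is always one day when this term is the smallest. In the Week 12 analysis that requires an extension dose on or before Day 85. Since only onset dates exist, an event dated on the dose day is treatment-emergent by the table and outside time at risk by 7.8.1.

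**After alignment.** With one end date for both, the difference is 0 days in every row, and with last contact as that date no day up to last contact lies outside a phase.

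**The case against.** The case that this is only wording has real force.

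- **The dates will usually coincide.** Protocol 3.1 ends participation at the last planned visit, and Protocol 5.2.6.2 describes follow-up as ending with an examination that it equates with the last per-protocol contact. This stands as a limit on size. The rule still has to work when the dates differ, which the table's follow-up row foresees.
- **Few events can fall in the gap.** After the end of trial, Protocol 5.2.6.2 asks only for drug-related serious events and drug-related events of special interest, on the SAE form and not the CRF. This stands too. What remains is mainly denominator time with nothing to count in it.
- **Phone contacts are weak evidence of later data.** Protocol 4.2.1 says that patients refusing to return "should at least provide safety information by phone at the respective visits". A patient with no EoS visit has no date for the third clause, so the phase runs to Day 113 and no gap arises.
- **The rate is internally consistent for roll-over patients**, because its numerator is restricted to time at risk. Correct: the disagreement is between the crude table and the rate table, on one calendar day.
- **All safety analyses are descriptive**, and individual data are listed. No test or error rate is affected.

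A reader might infer that the gap lowers the placebo rate in particular, since Protocol 3.1 allows an early EoS visit for Week 1 escape users. The documents do not say how many such patients there will be in each arm, or that their last contact would follow that visit, so no direction between arms can be claimed.

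**Conclusion.** The plan is wrong as written, with a small effect. Two sections of the SAP end the same randomized-treatment window on different dates, and nothing else in the documents reconciles them.

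Without roll-over, the rate is slightly diluted if last contact is later than an EoS visit held before Day 113. This adds up to 7 days per patient for an on-schedule visit after the Day 1 dose alone, more for an early discontinuer, and nothing when the dates are equal. With roll-over, events dated on the first extension-dose day can make the crude and rate tables differ. The number of patients affected is not known from the documents, and the dates in the table above are assumptions.

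Two wider readings are not supported. One is that the rates in general divide events from one window by time from another; the numerator wording in 7.8.1 rules that out. The other is that the periods after open-label or rescue spesolimab share the fault because their risk time can run past Day 113. Table 6.1: 1 is defined by randomized treatment, those periods have their own definitions in SAP 6.1, 7.8 and 7.8.1, and their technical detail is left to an ADS Plan that is not among the documents.

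**What to change.** Use one end date per patient for the randomized-treatment phase and for time at risk.

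- **Without roll-over:** replace the third clause of Table 6.1: 1 by the last contact date on the EoS page, which matches Protocol 7.3.5. Alternatively, if adverse event collection stops at the EoS visit, end time at risk in 7.8.1 at that visit and state how any event dated later is handled.
- **With roll-over:** apply one same-day rule for the first extension dose in both places. The day-prior convention that SAP 7.8 already uses for open-label and rescue doses would serve: the phase and the time at risk both end the day before, and a same-day event belongs to the new period.

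The cost is one or two lines of SAP text and one derived date in the analysis data set. No new data are needed. It is best done before unblinding.
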